1.7 Research Hypotheses

- Primary Hypothesis: Avelumab treatment will result in an increase in CD3+CD4+ T-cell and CD3+CD8+ T-cell infiltrates.
- Secondary Hypotheses:
 - Pathological response rate will be comparable to historical controls receiving NA cisplatin based chemotherapy.
 - 2 year disease free survival (DFS) will be better than historical controls not receiving NAC and comparable to historical controls receiving cisplatin based NAC.
 - Avelumab will be safe and tolerable in our patient population.
 - Infiltration of regulatory B-cells will increase with avelumab treatment and increased levels will be associated with less response to treatment.
 - Increased COX-1 and COX-2 levels on transurethral resection of the bladder tumor (TURBT) tissue will be associated with decreased response to avelumab.

1.8 Rationale for Conducting this Study

Up to 50% of patients are unable or unwilling to receive cisplatin-based NAC and their median DFS ranges from 12 to 48 months, compared to 48 months to > 5 years for those who receive cisplatin-based NAC. (60) Patients who are unable to receive cisplatin-based NAC go straight to RC. There is no approved NA systemic therapy for this population and survival outcomes are significantly inferior to those who receive cisplatin-based NAC. ICIs have been observed to be superior to non-cisplatin based chemotherapy in the first line setting for metastatic UCC and have shown significant efficacy after progression on platinum based chemotherapy in metastatic UCC. (28-34) Thus, there is rationale that ICIs may be of benefit in the NA treatment of MIBC patients who are not candidates for cisplatin-based NAC. We plan to examine this as one of our secondary endpoints in this window of opportunity trial.

1.9 Benefit/risk and Ethical Assessment

High grade (grade 3-4) AEs with PD-1 or PD-L1 inhibitors in metastatic UCC range from 5-22%, with such events being slightly lower in those who received PD-L1 as opposed to PD-1 inhibitory antibodies. (28-33) Our inclusion and exclusion criteria are in agreement with these previous studies and thus we expect to see a similar incidence of AEs. This estimated occurrence of high grade AEs is significantly less than the 50-80% seen with cisplatin-based NAC or with cisplatin-based chemotherapy in the metastatic setting. (11, 61-62)

We know that cisplatin-based NAC provides a significant survival benefit for non-metastatic MIBC and that ICIs are suggested to have similar or better efficacy than systemic chemotherapy in metastatic BC. Thus, the potential benefit to administering avelumab in the NA setting is significant. The benefit to risk ratio of this trial is judged to be acceptable.

1.9.1 Risks Associated with Avelumab

Three types of risks are associated with avelumab: general signs and symptoms, reactions that occur during or following the infusion, and immune side effects.

The following side effects have been observed among 1,738 patients treated with avelumab according to the results from two oncology clinical studies in patients with various solid tumors.

Side effects observed in 10% or more of patients:

- **General signs or symptoms:** Tiredness; Nausea; Loose or watery stools (diarrhea); Constipation; Reduced appetite; Decrease in weight; Vomiting; Low number of red blood cells (anemia); Belly pain; Cough; Fever; Shortness of breath; Swelling of feet and legs; Back pain; Joint pain.
- **Reactions that occur during or following the infusion:** may include chills or shaking, fever, flushing, back pain, belly pain, shortness of breath or wheezing, decrease in blood pressure, hives. These infusion reactions are mostly mild or moderate and generally resolve with a slowdown or discontinuation of the infusion and administration of medications such as anti-allergic and pain-killer drugs. In some cases these reactions may be severe or life-threatening (in less than 1% of patients) and can require intensive medical care.

Immune side effects

Immune side effects result from an increased activity of the immune system. Most of these side effects are reversible, which means they will stop once treatment with avelumab is discontinued. However, in some cases these reactions may be severe (approximately 2% of patients) and may lead to death in rare cases. The reactions that are more severe require treatment with drugs that decrease the immune system function, also called immunosuppressant drugs (like corticosteroids or more potent drugs). No immune side effects were observed in 10% or more of patients.

Immune side effects observed in 5% to less than 10% of patients:

- **Abnormal function of the thyroid gland (could include low or high function or inflammation of the thyroid gland):** may include rapid heartbeat; increased sweating; extreme tiredness; weight gain or weight loss; hair loss; changes in mood or behavior such as irritability or forgetfulness; feeling cold; constipation; voice gets deeper.
- **Inflammation of the skin (rash):** may include skin rash, itchy skin, skin redness, skin blisters, or peeling.

Immune side effects observed in 1% to less than 5% of patients:

- **Inflammation of the large intestine (colitis):** may include diarrhea (loose stools) or more frequent bowel movements than usual; blood in stools or dark, tarry, sticky stools; severe stomach area (abdomen) pain or tenderness.
- **Inflammation of the lungs (pneumonitis):** may include new or worsening cough, shortness of breath, chest pain.

Immune side observed in less than 1% of patients:

- **Inflammation of the liver (hepatitis):** may include yellowing of skin or of the whites of eyes; severe nausea or vomiting; pain on the right side of stomach area (abdomen); drowsiness; dark urine (tea colored); bleeding or bruising more easily than normal; feeling less hungry than usual.
- **Inflammation of the kidneys (nephritis):** may include urinating less than usual; blood in urine; swelling in ankles; loss of appetite.

- **Low function of the adrenal glands (glands on top of the kidneys), which may be due to the reduced function of the pituitary gland (a gland in the head):** may include very low blood pressure; extreme tiredness.
- **Increase in blood sugar (diabetes):** may include urinating more often than usual; feeling more hungry or thirsty than usual, nausea or vomiting, stomach area (abdomen) pain.
- **Inflammation of the eyes (uveitis):** may include changes in eyesight.
- **Inflammation of the muscles (myositis):** may include severe or persistent muscle or joint pain; severe muscle weakness.
- **Inflammation of the heart (myocarditis):** may include chest pain or tightness; tiredness; changes in heartbeat, such as beating fast, or seeming to skip a beat, or pounding sensation; swelling of feet and legs; trouble breathing.
- **Inflammation of the nerves (Guillain-Barre syndrome):** may include "pins and needles" sensations in arms and legs; weakness in legs that spreads to the upper body and may lead to temporary paralysis.

2. STUDY OBJECTIVES

2.1 Primary objective(s)

- To evaluate change in T cell subpopulations (CD8, CD4 and/or CD3) in tumor samples collected pre- and post-treatment with avelumab.

2.2 Secondary objective(s)

- To evaluate pathologic partial response (downstaging to < pT2) and complete response
- To evaluate 2 year DFS
- To evaluate safety of drug in the NA setting
- To evaluate correlation of translational studies with response parameters

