4. AEs = adverse events
5. AESIs = adverse events of special interest
6. BC = bladder cancer
7. BCM = Baylor College of Medicine
8. BSC = best supportive care
9. BTLA4 = B and T lymphocyte attenuator
10. C = Cycle
11. CBP = child bearing potential
12. CCL = C-C motif chemokine ligand
13. CD = cluster of differentiation
14. Chemo = chemotherapy
15. CMV = cisplatin + methotrexate + vinblastine
16. CT = computed tomography
17. CTCAE = common terminology criteria for adverse events
18. CTLA-4 = cytotoxic T-lymphocyte protein 4
19. CXCL = C-X-C motif chemokine ligand
20. D = day
21. DAMP = damage-associated molecular pattern
22. DFS = disease free survival
23. DLDCCC = Dan L Duncan Comprehensive Cancer Center
24. DSS = disease specific survival
25. ELISA = enzyme-linked immunosorbent assay
26. EPO = erythropoietin
27. FDA = federal drug administration
28. FFPE = formalin fixed paraffin embedded
29. FOXP3 = forkhead box P3
30. F/U = follow-up
31. GC = gemcitabine + cisplatin
32. G-CSF = granulocyte macrophage colony stimulating factor
33. GE = gastroesophageal
34. GM-CSF = granulocyte macrophage colony stimulating factor
35. ICI = immune checkpoint inhibitors
36. IDO = indoleamine 2-3 dioxygenase
37. IFN- γ = interferon gamma
38. IHC = immunohistochemistry
39. IRB = institutional review board
40. KIR = killer immunoglobulin receptor
41. LAG3 = lymphocyte activation gene 3
42. ICH = International Conference on Harmonization
43. ICOS = inducible T-cell costimulatory
44. IgG1 = immunoglobulin G1

45. IRB = institutional review board
46. iNOS = inducible nitric oxide synthase
47. IL = interleukin
48. m = months
49. mABs = monoclonal antibodies
50. M-CSFR = macrophage colony stimulating factor receptor
51. MDSCs = myeloid derived suppressor cells
52. MHC = major histocompatibility
53. MIBC = muscle invasive bladder cancer
54. MRI = magnetic resonance imaging
55. MVAC = methotrexate + vinblastine + adriamycin + cisplatin
56. NA = neoadjuvant
57. N/A = not available
58. NAC = neoadjuvant chemotherapy
59. NMIBC = non-muscle invasive bladder cancer
60. NSCLC = non-small cell lung cancer
61. NK = natural killer
62. ORR = overall response rate
63. OS = overall survival
64. PD-1 = programmed death 1
65. PD-L1 = programmed death ligand 1
66. PD-L2 = programmed death ligand 2
67. PGE2 = prostaglandin E2
68. PLND = pelvic lymph node dissection
69. PFS = progression free survival
70. pT0 = pathologic complete response
71. RC = radical cystectomy

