1. INTRODUCTION

1.1 Role of Neoadjuvant Chemotherapy in Muscle Invasive Bladder Cancer

Multiple clinical trials have shown improvements in overall survival (OS) and disease free survival (DFS) for patients with muscle invasive bladder cancer (MIBC) administered cisplatin containing neoadjuvant chemotherapy (NAC) when compared to radical cystectomy (RC) alone. (Table 1) (1-11) In these studies improved survival has been associated with lack of residual disease at the time of RC. (2-10) Additionally, multiple meta-analyses have shown significant benefits for cisplatin containing NAC when compared to RC alone. One of these meta-analyses consisted of 3005 patients across 11 trials; it showed 5 year absolute improvements for OS of 5% and DFS of 9%. (12)

Traditionally the NAC of choice was standard dose methotrexate + vinblastine + adriamycin + cisplatin (MVAC), but recently studies have suggested equivalency of gemcitabine + cisplatin (GC) and dose-dense MVAC. (Table 1) The three cisplatin containing NAC regimens recommended by the National Comprehensive Cancer Network include 1) dose-dense MVAC for 3-4 cycles, 2) GC for 4 cycles or 3) cisplatin + methotrexate + vinblastine (CMV) for 3-4 cycles. (13) The regimen we generally use neoadjuvantly for MIBC at Baylor affiliates is GC. These regimens and the data in Table 1 are for those with predominantly urothelial cell carcinoma (UCC), which is the majority of the patients seen in clinical practice and those that will be included in our trial. Perioperative recommendations for other histologies (e.g., squamous cell and adenocarcinoma) are different and are not discussed here since those patients without predominant UCC histology are excluded from participation in our trial.

Table 1: Studies of Cisplatin Containing Neoadjuvant Chemotherapy in Muscle Invasive Bladder Cancer

Study	Study Type	Patient Number	NAC Treatment	pt0 Rate	OS
Grossman HB et al.	Phase III RCT	317	3 cycles standard dose MVAC	a) NAC – 38%, p < 0.001 b) No NAC – 15%	c) NAC – median 77m, p = 0.05 d) No NAC – median 46m
BA06 30894 trial	Phase III RCT	976	3 cycles of CMV	a) NAC – 32.5% b) No NAC – 12.3%	c) NAC – 10 year 36%, HR 0.84, p = 0.037 d) No NAC – 10 year 30%
Pilimack ER et al.	Phase II	40	3 cycles of dose-dense MVAC	38%	N/A
Herchenhorn D et al.	Phase II	22	3 cycles of GC	26.7%	Median 36m

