3.4 Evaluability and Patient Replacement

Patients will continue to be enrolled on study until we have enrolled/treated 10 patients who are evaluable for the primary endpoint. Patients will be replaced after enrollment if they are later determined not to be evaluable for the primary endpoint.

Evaluable patients

- For primary endpoint
 - Receive \geq 1 dose of avelumab, undergo RC within 5 weeks of last dose of avelumab, and are not started on systemic steroids at a dose of > 10 mg/d of prednisone or equivalent, while taking avelumab.
- For safety endpoint
 - Receive \geq 1 dose of avelumab
- For pathologic complete response/partial response
 - Receive \geq 1 dose of avelumab and undergo RC < 42 days from last avelumab dose
- For 2 year disease free survival
 - Meet evaluability criteria for complete response/partial response, participate in 90 day on study follow-up after RC and participate in off study follow-up as part of regular care up to 2 years post RC.

Inevaluable patients

- Patients who receive < 1 dose of avelumab after study enrollment for any reason.

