4. SUBJECT SELECTION: PATIENT INITIALS: _____

4.1 Inclusion Criteria

- a) Have undergone TURBT showing newly diagnosed muscle invasive UCB (mixed histology is allowed if the predominant histology is UCC) within 6 weeks prior to cycle 1, day 1 of treatment.
- b) No prior systemic treatment for muscle invasive UCB
- c) Clinical T2-T4a disease
- d) No evidence of clinically positive lymph nodes or distant metastasis on computed tomography (CT) scans of chest and CT or magnetic resonance imaging (MRI) studies of the abdomen/pelvis. Imaging must be within 90 days of registration.
- e) Male or female subjects aged \geq 18 years old.
- f) Must have adequate kidney, liver, and bone marrow function within 30 days of registration, as follows:
 - a. Absolute neutrophil count (ANC) $\geq 1.5 \times 10^9/L$
 - b. platelet count $\geq 100 \times 10^9/L$
 - c. hemoglobin $\geq 9 \text{ g/dL}$ (may have been transfused)
 - d. Total bilirubin level $\leq 1.5 \times \text{ULN}$
 - e. AST and ALT levels $\leq 2.5 \times \text{ULN}$
 - f. Estimated creatinine clearance $\geq 30 \text{ mL/min}$ according to the Cockcroft-Gault formula
- g) Negative serum or urine pregnancy test at screening for women of childbearing potential (WOCBP), within 30 days of registration.
- h) Both male and female subjects must agree to use highly effective contraception (see Section 6.1 Table 8) while receiving avelumab and for at least 60 days after last avelumab treatment if the risk of conception exists.

Female patients must agree to inform study coordinator or investigator immediately if they think they have become pregnant during the study.
- i) Must have FFPE tissue available from the TURBT, and patient must consent to the use of tissue specimens from TURBT and RC for the study.
- j) Patients must have refused or have been determined to be ineligible for cisplatin-based NAC. Ineligibility criteria include: creatinine clearance $< 60 \text{ ml/min}$ by Cockcroft-Gault formula, CTCAE grade ≥ 2 hearing loss, CTCAE grade ≥ 2 neuropathy, and at discretion of medical oncologist.

If a patient is eligible for cisplatin-based NAC but has refused it, the reason for refusal must be documented in the patient record.
- k) Must be eligible for RC in the opinion of the treating investigator, and willing to undergo this procedure.
- l) ECOG performance status (PS) score of 0-2
- m) Signed informed consent form.

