7.2.2 Radical cystectomy

Radical cystectomy procedure is to be done per standard clinic practice.

In men this procedure involves removal of the bladder and prostate. In women it involves removal of the bladder and oftentimes a hysterectomy as well. In both sexes the procedure is followed by formation of a urinary diversion. The forms of urinary diversion include formation of an ileal conduit (where the ureters empty into the ileum) or formation of an internal reservoir, such as neobladder or continent cutaneous diversion. Relative contraindications to these internal drainage procedures include Tis in the prostatic ducts or a positive urethral margin. (63)

Bilateral pelvic lymph node dissection (LND) is considered standard of care and will be pursued in all patients with no set criteria for dissection template or number of LNs. Unusual circumstances, such as prior LND for another malignancy, significant scarring or inflammation, may preclude a full LND in some patients and will not qualify as a protocol deviation.

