10.2 Statistical analysis

To see the change in T cells pre- and post-treatment, paired t-test or nonparametric Wilcoxon signed rank test will be used after checking its normality.

Pathological response rate will be estimated along with 95% confidence interval. Two year disease free survival will be calculated using Kaplan-Meier survival curves with estimates of median and 95% confidence interval. Patients who are decided not to be evaluable for the primary outcome will be considered evaluable for the safety analysis and secondary outcomes, such patients will be summarized descriptively. The correlation of translational studies with response parameters will be summarized descriptively. Changes from pre- and post- treatment will be assessed using paired tests. SAS software will be used for all statistical analyses.

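### Pathologic response is set by bladder T stage alone, so a patient with positive pelvic nodes at cystectomy can meet the response criterion despite residual disease

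*Protocol*

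**What the plan says.** Protocol section 2.2 lists the objective as "To evaluate pathologic partial response (downstaging to < pT2) and complete response". The bracketed criterion belongs to partial response; complete response is named without one. The only meaning given for complete response is "pT0 = pathologic complete response", in the abbreviation list and again in the footnote to Table 1.

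Nodal status enters the protocol in two other places. Section 4.1 admits patients on imaging: "No evidence of clinically positive lymph nodes or distant metastasis on computed tomography (CT) scans of chest". Section 7.2.2 then plans nodal surgery: "Bilateral pelvic lymph node dissection (LND) is considered standard of care and will be pursued in all patients". It also says there are "no set criteria for dissection template or number of LNs", and that circumstances preventing a full dissection are not a protocol deviation.

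Section 3.4 makes a patient evaluable for response after at least one dose, if they "undergo RC < 42 days from last avelumab dose"; nodes are not mentioned. Section 10.2 gives the analysis: "Pathological response rate will be estimated along with 95% confidence interval". Section 1.7 expects the rate to be comparable with historical controls given cisplatin-based neoadjuvant chemotherapy.

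**The concern.** Negative nodes on imaging do not exclude microscopic nodal disease, so some entrants may prove node-positive at surgery. If the bladder specimen of such a patient is pT0 or pT1, the stated rule makes the patient a responder. That sits badly with the protocol's own background. Section 1.1 says of the chemotherapy trials: "In these studies improved survival has been associated with lack of residual disease at the time of RC". A patient with tumour in the pelvic nodes has residual disease at that time.

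Two results depend on the label. One is the response rate with its confidence interval. The other is the set of correlations between translational markers and response, which section 10.2 summarises descriptively and to which the regulatory B-cell and COX hypotheses of section 1.7 refer. The error runs in one direction: ignoring nodes can add responders but cannot remove any.

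**Working it through.** **Is a nodal condition stated anywhere?** The places where it could stand, side by side:

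- Objectives (2.2): T category for partial response; no criterion for complete response.
- Abbreviations and Table 1 footnote: complete response equals pT0.
- Evaluability (3.4): dosing and timing of surgery only.
- Study calendar (7.1): a pathology assessment, with no content specified.
- Surgery (7.2.2): node dissection planned, with no link to response.
- Statistics (10.2): a proportion with an interval, with no definition of a responder.

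None requires N0 or says how node-positive disease is classified. Bladder pT1 with positive nodes satisfies < pT2, and bladder pT0 with positive nodes satisfies pT0.

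**Is there a design figure to reproduce?** There is none for response: no target rate, threshold or power. The only design figure is the roughly 80% power for the primary endpoint (section 10.1). With r = 0.5, the SD of the paired difference is √(2 × (1 − 0.5)) = 1, so a 1 SD change with n = 10 gives noncentrality √10 = 3.16 on 9 degrees of freedom. A two-sided 5% paired t-test then has 80.3% power. The stated figure reproduces, and it does not involve the response definition.

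**Effect of one patient.** Input: 10 evaluable patients (section 3.1). One reclassification moves the rate by 1/10 = 10 points. Exact (Clopper-Pearson) 95% intervals for an illustrative case:

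| Rule | Responders | Rate | 95% CI |
|---|---|---|---|
| Node-positive patient not counted | 3/10 | 30% | 6.7 to 65.2% |
| Same patient counted | 4/10 | 40% | 12.2 to 73.8% |

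Sections 3.4 and 10.2 let some patients who are replaced for the primary endpoint still count for response. The response denominator n may therefore exceed 10, and the step is then 100/n points.

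**How likely is at least one such patient?** The documents give no frequency, so the share q of evaluable patients who are node-positive with bladder stage < pT2 is an assumption. The chance of at least one in 10 is 1 − (1 − q)^10, and the expected rise in the rate is 100q points.

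| Assumed q | Chance of at least one in 10 | Expected rise in rate |
|---|---|---|
| 2% | 18% | 2 points |
| 5% | 40% | 5 points |
| 10% | 65% | 10 points |
| 20% | 89% | 20 points |

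**The case against.** Several points on the other side have weight.

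- **Complete response is undefined in 2.2 rather than wrongly defined.** This stands. For complete response the point rests on a glossary entry and a table footnote. A SAP not at hand might add N0. For partial response, however, the protocol does state a criterion, and it is T-only; a later nodal requirement would change that criterion, not fill a gap.
- **Downstaging is ambiguous.** A patient who enters with clinically negative nodes and proves node-positive has moved up on N, and one could argue that this is not downstaging. But the threshold attached to the word is a T category, so the plain reading counts the patient. If two readings are open, that is itself a reason to fix the rule before results are known.
- **Table 1 reports pT0 with no nodal condition shown.** This is the strongest objection. Requiring N0 in this trial alone could spoil a like-for-like comparison with those rates. Whether the cited studies required N0 cannot be told from the documents. This argues for reporting both rates. It does not justify a T-only label in the marker correlations, and Table 1 has no < pT2 column.
- **Nodal status will be ascertained unevenly.** This is true, since section 7.2.2 sets no template or node count. It calls for a rule on incomplete dissection, not for ignoring nodes.
- **The effect is small and hypothetical.** The two illustrative intervals overlap almost entirely, and no test or decision depends on the rate. This stands and limits the weight of the point.

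A reader might infer more than the text supports: that response is a key endpoint, that it splits patients in every marker analysis, or that section 1.1 is the stated justification for it. The protocol never calls it key. It speaks of response parameters without specifying a responder split. Section 1.1 is background on chemotherapy trials.

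**Conclusion.** The point holds in a limited form. Partial response is defined by bladder T stage alone, and complete response is glossed only as pT0. A patient with pT0 or pT1 and positive nodes at cystectomy therefore meets the criterion as written, despite residual disease. At n = 10, each such patient adds 10 points to the rate and carries a wrong label into the descriptive correlations.

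A reader might go further and conclude that the reported rate will be inflated or that the historical comparison is invalid. The documents do not show either. They give no frequency of such patients, so there may be none among the 10, and the Table 1 rates may rest on the same T-only convention. The assumptions here are the plain reading of the T-category terms, 10 evaluable patients, and no nodal rule in a document not at hand. The primary endpoint and its power are untouched.

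**What to change.** In section 2.2:

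- Define complete response as pT0 N0.
- Define partial response as < pT2 N0 excluding pT0 N0, so that the two categories do not overlap, with overall response as their sum.
- Count any patient with positive nodes as a non-responder.
- Keep patients with no or limited node dissection in the denominator and classify them by a rule stated in advance. For example, where no positive node is found, classify by T stage and flag as pNx, with a sensitivity count that treats these patients as non-responders.

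In section 10.2, report the T-only pT0 rate beside the new rate, for comparison with Table 1.

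The cost is a few lines of text and one extra reported line. The surgery and its pathology are already planned; the data form needs to capture nodal stage, which the calendar does not name separately. The downside is that the response rate may come out slightly lower.
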